Peripheral blood will be collected for immunogenicity assays at baseline, then on Days 42, 70, and 98 (\pm 2 weeks). Tissue biopsies will be taken in each treatment group from consenting subjects before treatment and on Day 42, on Day 98 (\pm 2 weeks), at 6 months or longer (for patients with treatment response), and at the time of progression to assess immune cell invasion, including changes in PD-L1, CD4, CD8/Ki-67 and/or CD3/perforin expression. If a patient undergoes a tumor biopsy at any time after disease progression, investigators are strongly encouraged to provide biopsy tissue to the sponsor for immune response and tumor changes analysis.

Imaging will be performed approximately every 6 weeks for 12 months, then every 12 weeks for tumor staging until progression. Tumor responses will be assessed at the sites by evaluating tumor images/scans using RECIST modified to use irRC-specified confirmation and unidimensional tumor measurements. Adjudication will be performed by blinded independent central review (BICR) following the same rules. The irRC modification requires a confirmation of CR/PR/progressive disease (PD) at least 4 weeks later with imaging; once confirmed, the date of progression is defined as the first date that the total tumor burden was shown to have increased by at least 20% compared with the nadir.

Patients will be followed until confirmed radiographic disease progression to determine ORR and PFS. In addition, OS status will be followed up until the end of the trial. If the patient dies, the date of death will be documented by the local physician and/or registries.

All SAEs, DLTs, and MEOIs deemed potentially related to the study agents will be reviewed by the Sponsor and an independent Data Monitoring Committee (DMC).

Following completion of CMB305 dosing, patients will continue with clinical assessment and imaging approximately every 6 weeks until disease progression, as defined by RECIST (v1.1) modified to use irRC. The expected duration of a patient's participation in the trial is up to 2.1 years, including Screening, Treatment Phase, Booster Phase (for patients in the combined treatment arm), and Maintenance Phase (with follow-up visits until disease progression). Patients will then enter the Survival Follow-up Phase and their physicians will be contacted every 3 months by telephone to assess OS.

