5.7 Overall Study Duration and Follow-Up

The expected duration of patient participation on study treatment is 2.1 years. The study period will consist of Screening (study Day -30 to -1), Treatment Phase (study Days 0 to 84), Booster Phase (in the combined treatment arm) with continuation of G305 boosters (post Day 84 to 1 year [post Day 0] or until disease progression), Maintenance Phase with continuation of atezolizumab treatment (for the combined treatment arm, 1 year to 2 years [post Day 0] and, for the control arm, post Day 84 to 2 years [post Day 0], or until disease progression), and Survival Follow-up Phase (quarterly thereafter). The overall study duration will depend on speed of enrollment and time to the number of events.

Following completion of CMB305 dosing, patients will continue with imaging and clinical assessment every 6-9 weeks until disease progression, as defined by the RECIST v1.1 criteria modified to use irRC ([Section 6.3](#)). Patients or their physicians will then be contacted by the sites every 3 months by telephone to assess OS.

For patients receiving CMB305, blood will be collected to test for LV305 persistence at baseline and then at 6, 12, and 24 months following the first study treatment administration. Depending on the results from the 12-month sample, annual assessments may continue until 2 consecutive yearly samples show no evidence of LV305 persistence.

Patients with confirmed radiographic disease progression by irRC will be followed thereafter by the site every 3 months by contacting their primary physician by telephone as long as they are able to engage in follow-up until date of death recorded. Follow-up telephone contact will ascertain vital status, as well as possible occurrence of second malignancies and any SAE that might be possibly related to CMB305 treatment.

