8.2.3 Post-CMB305 Long-term Treatment Study Visits

Following the Treatment Phase, patients in the combined treatment arm will enter the Booster Phase (post Day 84 to 1 year post Day 0); patients who complete the Booster Phase will then enter the Maintenance phase (1 year to 2 years post Day 0). Patients in the control arm will enter the Maintenance Phase (post Day 84 to 2 years post Day 0).

8.2.3.1 Booster Phase (Combined Treatment Arm Only: post Day 84 to 1 year post Day 0)

The following procedures will be performed in the combined treatment arm during these visits:

1. AEs and SAEs (including MEOIs)
2. Concomitant Medications
3. Vital Signs
4. Physical examination: simple targeted examination
5. ECOG status
6. A G305 booster will be given in the combined treatment arm 6 weeks following the Day 84 dose and every 6 weeks thereafter for 1 year (from Day 0) or until disease progression.
7. Atezolizumab administration will be administered on Day 105 and every 3 weeks thereafter for 1 year (from Day 0) or until toxicity develops or progression. After Day 105, one of three atezolizumab doses may be delayed by 1 week (28 days instead of 21 days for one cycle) to allow for vacations.
8. Urine pregnancy test must be performed for FCBP within 72 hours before study drug administration and negative before study drug administration, if patients are still receiving booster doses of G305 and/or atezolizumab.

Blood samples for cellular immunity (55 mL) and a tumor biopsy will occur on Day 98 (\pm 2 weeks) and the following procedures will occur on Day 105:

- 12-lead ECG
- Blood for safety laboratory evaluations (10 mL)
- Urine pregnancy test for FCBPs
- Administration of atezolizumab

All subjects will return to the clinic every 3 weeks for 1 year (from Day 0) or until disease progression (whichever is later) for the following assessments:

1. AEs and SAEs (including MEOIs; only those possibly related to study drug will be reported)
2. Concomitant Medications (only those related will be reported)
3. Vital Signs
4. Physical Examination (symptom-specific)
5. ECOG status
6. Blood for safety laboratory evaluations (10 mL)
7. Thyroid function tests should be monitored at least every 3 months
8. Tumor staging by CT every 6 weeks for the first year, then every 12 weeks

The following procedures will occur at select study visits according to the study visit schedule provided in [Table 1](#):

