9.3 Efficacy Assessments

9.3.1 Tumor Response Based upon RECIST and irRC

Tumor staging by CT will be performed every 6 to 9 weeks and images/scans will be evaluated by the sites for treatment decisions and later by BICR for tumor responses. The RECIST v1.1 criteria modified to use irRC³⁷ will be used to determine disease progression as defined in [Appendix C](#). The irRC also require a confirmation of CR/PR/PD at least 4 weeks later with imaging. Once confirmed, the date of progression will be defined as the first date that the total tumor burden was shown to have increased by at least 20% compared with nadir. For this study, the modified irRC using unidimensional measurements of the tumor will be implemented (see [Appendix C](#) and [Appendix D](#)). Evaluations will be used for determination of PFR, PFS, ORR, DOR, and time to response. OS will also be evaluated.

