10.2.2.4 Efficacy Analyses

10.2.2.4.1 Primary Efficacy Analysis

The primary efficacy analysis will be the evaluation of OS and PFS based on the ITT Population.

Overall survival is defined as the time interval from randomization to death of any cause. Patients who are alive will be censored at the last known date alive or data analysis cutoff date, whichever is earlier. PFS is defined as the time interval from randomization to tumor progression or death. Accordingly, the precise definition of progression and the timing of imaging scans to progression are very important. Every effort must be made to assure that timeframes for follow-up imaging scans are achieved, so that both treatment groups can be usefully compared. Assessments must be adequate to evaluate target lesions, non-target lesions, and to search for new lesions.

PFS will be based on RECIST 1.1 response guidelines modified to use irRC-specific confirmation. PFS will be defined as the time from randomization to disease progression or death (any cause), whichever occurs first. The irRC modification requires a confirmation of progressive disease (PD) at least 4 weeks later with imaging; once confirmed, the date of progression is defined as the first date that the total tumor burden was shown to have increased by at least 20% compared with the nadir. Patients who do not have disease progression or have not died will be censored at the date when the last tumor assessment determines a lack of progression. If a patient begins a new anti-cancer therapy or has radiotherapy or surgery at a lesion site prior to confirmed progression (or death), the patient will be censored at the last assessment where the patient was documented as progression free prior to the intervention. Patients with two or more missing response assessments prior to a visit with progression (or death) will be censored at the last visit where the patient is documented to be progression free.

The primary efficacy analysis will be the evaluation of OS and PFS using Kaplan-Meier methodology and will be performed on the ITT Population for each treatment arm. Kaplan-Meier plots and 95% confidence intervals (CIs) for 75%, 50% and 25% survival, if reached, will be provided for each treatment group.

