10.3 Interim Analysis

An exploratory analysis of the PFR at 6 months after treatment initiation will be used as a non-binding futility analysis for each treatment arm. Upon obtaining the progression status after 6 months on study from the first 36 (18 per arm) and subsequently from all enrolled patients, interim analyses will be performed and presented to the DMC, which will include estimates of PFS and assessment of PFR. Based on the assumptions in Section 10.3.1, futility guidelines at Stage 1 will be based on 18 patients and will require at least 6 patients to be progression free to

continue on to Stage 2. With an additional 22 patients at the end of Stage 2, at least 14 of the total of 40 patients should be progression free at 6 months after initial dosing to recommend further study in this setting. No formal interim analysis will be performed for efficacy. For the purposes of safety monitoring, key safety analysis will also be performed quarterly. The DMC will evaluate the available data and make necessary recommendations to the study. Details will be outlined in the DMC charter.

A final analysis will be conducted when at least 72 deaths have been observed, or sooner if the Sponsor so decides.

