#### IMDZ-C232

Peripheral blood will be collected for immunogenicity assays at baseline, then on Days 42, 70, and 98 ( $\pm$  2weeks). Tissue biopsies will be taken in each treatment group from consenting subjects before treatment and on Day 42, on Day 98 ( $\pm$  2 weeks), at 6 months or longer (for patients with treatment response), and at the time of progression to assess immune cell invasion, including changes in PD-L1, CD4, CD8/Ki-67 and/or CD3/perforin expression. If a patient undergoes a tumor biopsy at any time after disease progression, investigators are strongly encouraged to provide biopsy tissue to the sponsor for immune response and tumor changes analysis.

Imaging will be performed approximately every 6 weeks for 12 months, then every 12 weeks for tumor staging until progression. Tumor responses will be assessed at the sites by evaluating tumor images/scans using RECIST (v1.1) modified to use irRC-specified confirmation and unidimensional tumor measurements. Adjudication will be performed by blinded independent central review (BICR) following the same rules. The irRC modification requires a confirmation of CR/PR/progressive disease (PD) at least 4 weeks later with imaging; once confirmed, the date of progression is defined as the first date that the total tumor burden was shown to have increased by at least 20% compared with the nadir.

Patients will be followed until confirmed radiographic disease progression to determine ORR and PFS. In addition, OS status will be followed up until the end of the trial. If a patient dies, the date of death will be documented by the local physician and/or registries.

All SAEs, DLTs, and medical events of interest (MEOIs) deemed potentially related to the study agents will be reviewed by the Sponsor and an independent Data Monitoring Committee (DMC).

Following completion of CMB305 dosing, patients will continue with clinical assessment and imaging approximately every 6 weeks until disease progression, as defined by RECIST (v1.1) modified to use irRC. The expected duration of a patient's participation in the trial is up to 2.1 years, including Screening, Treatment Phase, Booster Phase (for patients in the combined treatment arm), and Maintenance Phase (with follow-up visits until disease progression). Patients will then enter the Survival Follow-up Phase and their physicians will be contacted every 3 months by telephone to assess OS.

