- g. Imaging will be performed by CT scan as defined by RECIST/irRC at screening and every 6 weeks after first study injection for the first year, then every 12 weeks for tumor staging until disease progression and includes a confirmatory scan performed at least 4 weeks later. Magnetic Resonance Imaging (MRI), bone scans, or PET/CT at baseline or subsequent visits will be performed only if clinically indicated.
- h. An HIV screening test will be repeated on Day 168 to determine if seroconversion has occurred following LV305 injections. If positive, further testing can demonstrate that the normal complement of HIV proteins is not present (unless the patient has developed a true HIV infection).
- i. Blood for immunogenicity will be collected at clinical sites that are trained in peripheral blood mononuclear cells (PBMC) isolation. Baseline samples will be drawn twice to ensure a good yield. At least 55 mL should be collected in 8 Cell Preparation Tubes (CPT)TM tubes for T-cell response assays. See the Lab Manual for processing details.
- j. Initial safety labs are to be performed within 4 days before treatment initiation. On treatment days during the study dosing period, the hematology and clinical chemistry laboratories must also be performed and reviewed before dosing and may be performed up to 48 hours prior to the planned dosing.
- k. Thyroid function tests (triiodothyronine [T3], thyroxine [T4], and thyroid stimulating hormone [TSH]) should be taken at initial screening and at least every 3 months while being treated with atezolizumab. As thyroid disorders could occur at any time as a result of atezolizumab treatment, patients should be monitored for changes in thyroid function for clinical signs and symptoms of thyroid disorders (at the start of treatment, periodically during treatment, and as indicated based on clinical evaluation).
- Urine pregnancy test must be performed for women of childbearing potential within 72 hours before study drug administration and negative before study drug administration, including during the follow-up period if patients are still receiving booster doses of G305 and/or atezolizumab. Serum pregnancy test may be performed if the site's standard operating procedures allow.
- m. Booster doses of G305 will be given 6 weeks following the Day 84 dose and every 6 weeks thereafter for 1 year (from Day 0) or until disease progression at the staging visits.

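### Protocol 5.7 and 9.3.1 allow scans every 6 to 9 weeks against 6 weeks elsewhere in year 1, and the SAP's 91-day limit for censoring deaths in PFS does not fit its own 12-weekly scans after year 1

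*Protocol*

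**What the plan says.** **Imaging interval.** Two places in the protocol give a range. Section 5.7, on the period after CMB305 dosing: "patients will continue with imaging and clinical assessment every 6-9 weeks until disease progression". Section 9.3.1, with no period stated: "Tumor staging by CT will be performed every 6 to 9 weeks".

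The other places give 6 weeks in year 1. Protocol 8.2.3: "Tumor staging by CT every 6 weeks for the first year, then every 12 weeks". SAP 3.1: "Imaging will be performed approximately every 6 weeks for 12 months, then every 12 weeks for tumor staging until progression". SAP Table 1, footnote g: "every 6 weeks after first study injection for the first year, then every 12 weeks for tumor staging until disease progression". The synopsis, Protocol 8.2.2 and the protocol's own Schedules of Events agree. Protocol 5.1 has a sentence parallel to the one in 5.7, but with 6 weeks: "Following completion of CMB305 dosing, patients will continue with clinical assessment and imaging approximately every 6 weeks until disease progression". The Schedules allow tumor assessments a window of 1 week either way.

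**Missed assessments.** For PFS, the main text of SAP 5.1.1.1 censors a patient at the last progression-free visit when at least two response assessments were missed before progression or death. Table 3 uses the same count. One of the bullets that introduce Table 3 adds a day figure in parentheses: deaths after at least two missed assessments are taken as those more than 91 days after the last one.

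**The concern.** Progression is dated to the first scan that shows it, so the interval between scans enters PFS, a primary endpoint, and the Kaplan-Meier estimate of the 6-month progression-free rate. Protocol 10.2.2.4.1 says so itself: "the precise definition of progression and the timing of imaging scans to progression are very important". In an open-label trial, a range of 6 to 9 weeks leaves sites a choice that could differ between patients or arms. The precedence clause in SAP 8 covers statistical analysis text and does not tell sites when to scan.

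The 91-day figure is a separate problem and would remain if the 6-to-9-week wording were removed. It is a fixed number, while the schedule changes from 6 to 12 weeks after year 1. The same SAP section can therefore classify one death in two ways. Duration of response and duration of clinical benefit take their censoring from PFS (SAP 5.1.3.2 and 5.1.3.3), so they inherit the ambiguity.

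**Working it through.** **Inputs.** Year-1 interval 6 weeks = 42 days and later interval 12 weeks = 84 days (SAP 3.1, Schedules of Events). Range 6 to 9 weeks, so up to 63 days (Protocol 5.7, 9.3.1). Window 7 days (Schedules, footnote a). Limit 91 days (SAP 5.1.1.1). Median PFS 3 and 5.2 months, exponential, 40 patients per arm (SAP 4). Month = 30.4375 days (SAP 5.1.1.1).

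**1. Can the window explain the range?** No. Six weeks plus or minus one covers 5 to 7 weeks, not 9.

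**2. Reproduce the 91 days.** The SAP gives no derivation. Two intervals plus one window gives 2 x 42 + 7 = 91, an exact match for 6-weekly scans. The derivation is inferred, but the match is exact.

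**3. Apply the same formula to the other intervals.**

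| Interval | One interval + window | Two intervals + window |
|---|---|---|
| 6 weeks | 42 + 7 = 49 | 2 x 42 + 7 = **91** |
| 9 weeks | 63 + 7 = 70 | 2 x 63 + 7 = 133 |
| 12 weeks | 84 + 7 = **91** | 2 x 84 + 7 = 175 |

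After year 1, day 91 is when the first missed scan leaves its window. The second leaves its window only at day 175.

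**4. One death, two outcomes.** Take a year-2 patient who misses one 12-weekly scan and dies 120 days after the last scan, without documented progression. One scan is missed (due day 84); the next is due on day 168. By the count, in the main definition and in Table 3, the death is a PFS event. By the day limit (120 > 91) it is censored at the last visit. The same holds for any death on days 92 to 175, where at most one scan has definitively been missed.

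**5. How many patients could be exposed?** Progression free at 12 months: 0.5^(12/3) = 0.0625, or 2.5 of 40; 0.5^(12/5.2) = 0.202, or 8.1 of 40. So about 3 to 8 per arm are at risk when the 12-weekly schedule begins.

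**6. Sensitivity illustration for the 6-month rate.** Six months is 6 x 30.4375 = 182.6 days. With 6-weekly scans the last one before that is week 24 (day 168). With scans at the 9-week limit from week 12 it is week 21 (day 147), and the next is week 30. The protocol's rule is that "at least 14 of the total of 40 patients should be progression free at 6 months after initial dosing to recommend further study". At a true rate of 25%, the exact binomial chance of at least 14 of 40 is 0.103 with stage 1 non-binding, or 0.080 with stage 1 enforced. Suppose 25% is the rate read at day 168 and every patient is at the 9-week limit. The reading becomes 0.25^(147/168) = 0.297 and the chance 0.284 (0.228 enforced). If only 25% or 50% of patients are at that limit, it is 0.139 or 0.181 non-binding. These shares are assumptions.

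**The case against.** On the interval, the protocol comes close to resolving the conflict. Section 9.1 sends the reader to the Schedules of Events and Section 8.2 for the timing of assessments, 8.1 does the same for visits, and both sources say 6 weeks in year 1. In the combination arm, G305 boosters are given every 6 weeks in year 1 to coincide with staging. Section 5.7 applies only after CMB305 dosing is complete; if boosters count as CMB305 dosing, it may not reach month 6 in that arm. Against that, 8.2.3 heads the visits after Day 84 as post-CMB305, and 9.3.1 has no such condition. What stands is that 5.7 and 9.3.1 are isolated outliers, not a rival schedule.

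On the limit, the day figure is one parenthesis, introduced for use as needed, while the main definition and Table 3 use only the count. That narrows the problem, but a programmer who applies the parenthesis would still censor deaths that the main definition keeps.

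A reader might go further and infer that the interval conflict seriously weakens the 14-of-40 rule. The documents do not support this. The figure of 0.284 needs every patient at the 9-week limit, against the Schedules and the booster timing. It also sets 25% at day 168, which implies a median of 84 days (2.76 months), not the SAP's 3 months. If 25% is instead the true rate at 6 months, 6-weekly scans alone read 27.9% and give 0.204 non-binding (0.162 enforced), but that effect does not come from the inconsistency. The rule is exploratory, non-binding and applied per arm.

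**Conclusion.** Both points hold as wording faults with limited reach. Protocol 5.7 and 9.3.1 conflict with the 6-week interval that the rest of the protocol and the SAP set for year 1, and a 1-week window does not bridge the gap. The 91-day limit fits 6-weekly scans only. Under the SAP's own schedule after year 1, it censors deaths on days 92 to 175 after the last scan that the main definition and Table 3 count as events.

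The size is likely small. The 3 to 8 of 40 per arm are patients at risk, and it would be wrong to read them as patients misclassified. To be affected, a patient must miss a year-2 scan and then die without documented progression before a second scan is definitively missed. The documents give no basis for estimating how often that happens. The count at risk rests on exponential PFS with the planned medians, and 175 days rests on reading 91 as two intervals plus one window. Nothing here shows the 40 patients per arm to be wrong. The illustration for the 14-of-40 rule depends on assumed scan timing and is not the reason for the change.

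**What to change.** 1. Reconcile Protocol 5.7 and 9.3.1 with the synopsis, Protocol 5.1, 8.2.2, 8.2.3, both Schedules of Events and the SAP, so that one year-1 imaging interval applies in both arms. The sentence in Protocol 5.1, repeated in SAP 3.1, that continues 6-weekly imaging until progression should carry the change to 12 weeks that the same sections state.
2. In SAP 5.1.1.1, either make the limit follow the interval in force (2 x interval + 7 days: 91 for 6-weekly, 175 for 12-weekly), or delete the day figure and keep only the count. The count alone is simpler: it needs no rule for the change from 6- to 12-weekly scans, and the SAP already uses it without a day figure for DMFS.

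The cost is wording in the protocol and SAP, with no added patients and no change to the 14-of-40 bar. The downside is that a few year-2 deaths that the 91-day limit would censor become PFS events.
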